#### 2. Background and Rationale

Internationally, there is an increasing shift towards non-standard forms of work such as temporary work(1) and more people have 'portfolio' careers which involve them working for shorter periods or concurrently across different organisations, often without a conventional employment relationship.(2) In the healthcare sector, doctors working in temporary positions are usually referred to as locums, and the numbers and proportions of doctors working as locums in the NHS in England have grown substantially over the last decade. Between 2009 and 2015, the use of locums in NHS hospitals almost doubled(3) and between 2015 and 2019 the number of locums working in primary care increased by 250%.(4) In 2018, 8,810 doctors were registered with the GMC as working primarily as a locum, representing 3.6% of all registered doctors, but many more undertake some locum work alongside more conventional permanent employment.(5)

Locum doctors are essential for maintaining continuity of service as healthcare organisations use them to cover gaps in rotas due to absence or recruitment and retention problems, and also to fill service gaps in underserved or shortage specialties and areas. However, rising locum numbers and the associated increase in cost has led to a growing concern among policymakers, employers and professional associations about locum use.(68) Medical agency staff were estimated to have cost the NHS £1.1 billion in 2015/16,(9) and a locum pay cap was introduced in 2015 to curb expenditure.(10)

Some high profile examples of locum failures in care over recent years have contributed to widespread concerns about the quality and safety of locum doctors.(11-13) Locum doctors are often perceived negatively by patients,(6) other healthcare professionals (7) and NHS leaders.(8) They are often regarded as less professional (14) or as untrustworthy 'outsiders' who lack commitment and have poor intentions toward the organisation.(15, 16)

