#### **Primary care**

We will use the Clinical Practice Research Datalink (CPRD) to access electronic health records (EHRs) from primary care practices. The database holds anonymised general practice records on all registered patients, including diagnoses, test, prescribed treatments and referrals. Each interaction with a health professional is recorded, through unique identifiers for patients, consultations and health professionals. The staff role field can be used reliably to identify the type of GP (partner, salaried, or locum) involved in any recorded interaction. In addition, linkage to Hospital Episodes Statistics (HES) data is available. This allows us to obtain detailed information on any form of hospital attendance for all patients in the practices that are part of this linkage scheme. Our proposal plans to use data from both CPRD Gold (practices using Vision software) and the more recent CPRD Aurum (practices using EMIS). In total we should be able to access data from about 1,100 practices for a median period of 10 years, involving millions of patient, the great majority of which have given permission for the practice data to be linked to HES.

We will analyse the data in bins of financial years. Within each financial year, our population will comprise of patients registered with a CPRD general practice for whole of the year. Preliminary analyses in CPRD have confirmed that the available staff role identifier is widely and reliably used across practices, and we will use it to identify locum and permanent GPs. This will be our key parameter of interest and we will evaluate its association with important patient outcomes. All analyses will be conducted at the patient level.

We will focus on service utilisation and patient outcomes. Our primary outcomes will be patients revisiting the general practice within 7 days or 15 days. Secondary outcomes will include: referrals to secondary care, unplanned hospital admissions within 7 days or 15 days (through HES linkage), A&E attendance within 7 days or 15 days (through HES linkage), ambulatory care sensitive conditions (ACSC) hospitalisations within 7 days or 15 days (through HES linkage), antibiotic prescriptions, and validated prescribing safety indicators (as established measures of clinical performance and quality of care) which we have already used in a prior study using the CPRD.(44)

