All analyses will be controlled for available patient, general practitioner and general practice characteristics. Patient: age, sex, deprivation as measured by the 2015 Index of Multiple Deprivation (IMD, in quintiles),(45) years registered with the practice (if not collinear with age), number of practice visits in the previous financial year (or in the previous 12 months since the current consultation event) and numerous chronic conditions which are well recorded in these databases since they are part of the Quality and Outcomes Framework (atrial fibrillation, asthma, cancer, coronary heart disease, chronic kidney disease, chronic obstructive pulmonary disease, dementia, depression, diabetes, epilepsy, heart failure, hypertension, limiting disabilities, severe mental health, osteoporosis, peripheral arterial disease, rheumatoid arthritis and stroke).(46) General practitioner: sex/age are unavailable, but see analytical plan below). General practice: list-size, urban/rural location, practice location IMD (in quintiles), region, ratio of locum consultations over total within the

respective analysis year. We will also derive and describe consultation characteristics, like type, length and day of the week, although these will be used for descriptive purposes.

Our power calculation is based on the primary outcome, revisiting general practice within 7 days, and on the assumption that 10% of patients consulting a permanent GP return within that time period. Assuming 9 consultations with a permanent GP for 1 consultation with a locum, an alpha level of 5%, and an increase in the outcome to 15% for locum consultations (OR=1.59), we would need a total of 4330 patients to have 90% power to detect the association. Although this approach ignores between-practice variability in both the intercept and the association (e.g. varying return rates for permanent GPs and locus), it does demonstrate that we have many hundreds (if not thousands) times the numbers needed to detect a meaningful association.

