All outcomes and key covariates of interest will be appropriately described over time, at the patient, GP and general practice level. For example, we will plot the percentage of revisits within 7 days by locum/permanent GP groups, across all practices, over time. We will use multi-level mixed effects logistic regression models to quantify the association between the exposure of interest (locum/permanent GP) and the outcomes of interest, controlling for all available covariates previously discussed. If an outcome (e.g. safety indicators) in better expressed as a count, e.g. if we identify that numerous indicators tend to apply to visits, we will use multi-level mixed effects Poisson or negative binomial regression models instead. Analyses will be conducted at the patient level, accounting for the nested structure of the data: patients within general practices, within regions. We will include random effects for practices and possibly for regions (alternatively a fixed effect for regions).

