We will use two designs to reliably evaluate the association of interest. Within each financial year, we will randomly select one consultation for each patient, and then align all the outcomes and covariates to that specific event date for the patient. This will allow us to give equal weights to patients, and limit the potential for confounding introduced by patients with very poor health who may be visiting numerous times within a year. The first design, will involve a multi-level regression on all randomly selected consultation events, which will be used to obtain adjusted estimates for the exposure of interest. The second design will involve an additional step before the regression analysis, propensity score matching. This approach will attempt to select two patient samples for each exposure group (locum/permanent GP) that are as "close" and comparable as possible, in terms of all their available characteristics. We will use logistic regression to obtain the propensity score for each patient within a financial year, the probability of membership to each exposure group (locum/permanent GP) given the observed covariate values. The score will then be used to match patients in the two groups of interest, using their propensity scores (10 in the permanent GP group to 1 in the locum group – with no replacements). The propensity scores will be plotted over time and the performance of the matching process will be evaluated. Next, the matched sub-samples will be analysed with the multi-level regression models previously described. Our primary analyses will be the unmatched regressions, since our group has conducted methodological work that has demonstrated that matching can be detrimental in large samples (the methods work well for small and very small samples), while the recommended conditional regression approach for matched samples does not

confer any benefits (while it's less flexible when it comes to modelling the nested structure of the data).

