Data will be complete (e.g. a patient either is coded as having diabetes or not) and of high quality since tied to financial incentives (e.g. QOF) or almost impossible not to record (e.g. consultation, or prescribing). Therefore, we will not need to use a multiple imputation framework or anything similar. Confounding is a concern, with urgent requests perhaps being more likely handled by locums – e.g. a patient cannot afford to wait for 2 weeks before his/her regular GP is back from holiday. We will partly attempt to control for that through the available patient characteristics, but we will also interpret our results with caution and use the recently suggested E-Value to assess the potential effect of unmeasured confounding.(47) The age of GPs is not available in the database, and another concern is that locums may be much less experienced that permanent GPs, hence any potential differences could be attributed to that rather than the locum status. Although we need to be careful not to "overcontrol" the analyses for the characteristics of locum GPs, since numerous GPs close to or in retirement choose to locum, we will conduct a sensitivity analysis where we will exclude more experienced permanent GPs (thus focusing on GP registrars, salaried GPs and GP retainers vs locums, repeating all analyses previously described).

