First, we will focus on prescribing activity which can be linked to a single locum. Specifically, by comparing prescribing practices using both established prescribing safety indicators developed for primary care but adapted for this setting(50) and EPR data on rates and outcomes of clinical pharmacist reviews/interventions (i.e. if the prescription is changed). Multivariate regression analysis will be used and safety indicators /pharmacist review outcomes will be the dependent variable. The independent variable will be binary, indicating whether the activity was performed by a locum. We will control for patient and ward characteristics which may be prescribing outcomes and treatment by locum (for example age, gender, speciality).

Our second approach will consider each entire patient admission and approximate the proportion of care delivered by locum doctors. For example if during their admission a patient has two interactions (such as tests or prescriptions) recorded by a locum doctor but six ordered by a permanent doctor, the proportion would be 0.25. This measure will be used as the independent variable when examining length of stay, rates of emergency readmission and mortality. With this analysis occurring in one trust only we will carefully consider if we have the power to detect meaningful associations. If under-powered, the processes developed could be applied to more trust EPR data in the future. Indeed, having undertaken this work successfully with Salford Royal NHS Foundation Trust, we will if time and resources allow seek to extend it to other hospitals in the Northern Care Alliance Group with similar EPR capabilities.

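### The plan names urgency of the consultation as a possible confounder of the locum effect but keeps its closest recorded proxies, consultation type and day of week, out of the models

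*Protocol*

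**What the plan says.** All of this is in Protocol section 5, WP4, Primary care.

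- **Adjustment set.** "All analyses will be controlled for available patient, general practitioner and general practice characteristics". The patient list covers age, sex, deprivation, years registered, earlier visits and chronic conditions. The practice list covers list size, location, deprivation, region and the practice's locum share of consultations in the analysis year.
- **Consultation characteristics.** These will be derived, "like type, length and day of the week, although these will be used for descriptive purposes".
- **Outcome model.** A multilevel logistic model, "controlling for all available covariates previously discussed". This points back to the lists above and brings in no consultation-level term.
- **Primary design.** "a multi-level regression on all randomly selected consultation events", with one consultation drawn per patient per financial year. The second design matches on a propensity score first and then fits the same models.
- **Confounding.** "Confounding is a concern, with urgent requests perhaps being more likely handled by locums". The example given is a patient who cannot wait for the regular GP to return from holiday. The response is partial control through patient characteristics, cautious interpretation and an E-value.

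**The concern.** Urgency belongs to the consultation. The same patient, with the same age, conditions and visit history, may attend once for an urgent problem and once for a routine one. Patient covariates can pick up who tends to need urgent care, but not whether the sampled contact was urgent. Consultation type and day of week vary at the right level and will already have been derived, yet they are reserved for description and no reason is given.

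The other planned steps do not fill this gap:

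- Matching uses patients' available characteristics and leads to the same models.
- The sensitivity analysis that drops more experienced permanent GPs addresses experience.
- The practice's annual locum share is the same for every consultation in a practice-year, so it cannot separate urgent from routine contacts within one.
- The E-value asks how strong an unmeasured confounder would have to be. It does not replace adjustment for what is recorded.

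At stake is how the main result is read. A modest excess of revisits after locum consultations could reflect the kind of request locums are given.

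**Working it through.** **The plan's own yardstick.** The power paragraph takes 10% revisits for permanent GPs and 15% for locums. OR = (0.15/0.85)/(0.10/0.90) = 1.588, which matches the stated 1.59. A two-sided Wald calculation on the log odds ratio at 9:1 allocation gives 4432 patients against the stated 4330, which is 2.4% more. The sample size does not bear on this point; 1.59 serves only as a scale, with ln 1.59 = 0.464.

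**Confounding by urgency with no locum effect.** The protocol gives neither the urgent share nor the revisit risk by urgency, so these inputs are assumptions:

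- Urgent share u: 40% or 50% for locums, 20% or 25% for permanent GPs.
- Revisit risk: 16% or 18% if urgent, 8% if not, whichever doctor is seen.

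The revisit rate in a group is u × r(urgent) + (1 − u) × r(routine).

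| Case | Locum rate | Permanent rate | Apparent OR | Share of ln 1.59 |
|---|---|---|---|---|
| Lowest: 40% v 25%, 16% v 8% | 0.40×0.16 + 0.60×0.08 = 11.2% | 0.25×0.16 + 0.75×0.08 = 10.0% | (0.112/0.888)/(0.10/0.90) = 1.135 | 0.127/0.464 = 27% |
| Highest: 50% v 20%, 18% v 8% | 0.50×0.18 + 0.50×0.08 = 13.0% | 0.20×0.18 + 0.80×0.08 = 10.0% | (0.130/0.870)/(0.10/0.90) = 1.345 | 0.296/0.464 = 64% |

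The other six combinations lie between these. A wider grid holds permanent revisits at 10% and the permanent urgent share at 20%, with a locum urgent share of 30% to 60% and an urgent-to-routine risk ratio of 1.25 to 3. It gives 1.03 to 1.68. The size therefore depends heavily on inputs that nobody has yet measured.

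**Precision gives no protection.** The protocol speaks of millions of patients. Assume 5 million, split 9:1, with 10% revisits and clustering ignored. The smallest log OR detectable with 90% power is 3.2415 × √(1/(500,000×0.09) + 1/(4,500,000×0.09)) = 0.0161, an OR of 1.016. An urgent share of 27% for locums against 25% for permanent GPs (16% v 8% revisits) gives 10.16% against 10.0%, an OR of 1.018. A two-point difference in urgency would already be detectable as a locum effect.

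**What imperfect proxies could recover.** Suppose a proxy identified urgency with 70% sensitivity and 90% specificity (assumed). Stratifying on it, with a Mantel-Haenszel summary, reduces 1.135 to about 1.08 and 1.345 to about 1.21. That removes a little over a third of the bias on the log scale, and the rest stays.

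**The case against.** **The plan is open about the problem.** It calls its control partial, promises cautious interpretation, plans an E-value and draws one consultation per patient-year to limit the weight of frequent attenders. Patient covariates may remove part of the urgency effect. This stands, and it lowers the severity, but it does not explain why recorded consultation variables are left out.

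**Type and day of week are not urgency.** The protocol does not say that type records urgency or list its categories, and day of week is a weak proxy. Type may also partly reflect the role locums are given. The figures above treat urgency as fully observed and the patient covariates as removing none of it. This stands too: the range bounds total urgency confounding and does not measure the gain from the fix.

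**Stronger readings the document does not support.**

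- A reader might infer that calendar trends also stay in the locum effect, since year is not a listed covariate and Protocol section 2 reports that "between 2015 and 2019 the number of locums working in primary care increased by 250" per cent. But "We will analyse the data in bins of financial years", and both sampling and propensity scores work within a financial year. In a fit by year there is no between-year bias. In a pooled fit, the practice's locum share for the analysis year makes the contrast essentially one within practice-years. In simulations with no true effect and assumed trends, crude odds ratios of 1.03 to 1.18 fell to between 0.98 and 1.01 once that share was included. All that is left is wording: the text could say whether the primary regression is fitted by year or pooled.
- A reader might extend the point to the hospital prescribing models, where "We will control for patient and ward characteristics". The examples that follow are an open list in a feasibility study, so the text does not exclude timing variables.
- A reader might take urgency to be the main confounder. The protocol does not rank it, and it raises GP experience as another concern.

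**Conclusion.** The point holds for urgency in the primary care analysis. The protocol raises the concern, will derive the nearest recorded variables and assigns them to description. That is a stated choice, not detail left for a later document. Under the main assumptions, total urgency confounding would produce an odds ratio of about 1.14 to 1.34 with no true locum effect. This is an upper limit, on those inputs, on what adding the proxies could remove; the actual gain is unknown and probably smaller. It should be fixed as a cheap improvement before the models are final. It does not invalidate the design.

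**What to change.** Add consultation type, day of week and month to the outcome model and to the propensity model; month is included because the protocol's own example is holiday cover. If the primary model is to stay as it is, put these terms in a pre-specified sensitivity model. Report the locum odds ratio with and without consultation type. Keep consultation length out of the adjustment, since the doctor influences it.

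The cost is a few extra terms per model and no new data, because the variables will be derived anyway. The limits should be stated with the result: type is an imperfect proxy, may be coded differently between practices and may partly reflect the locum's role. The change reduces the bias and does not remove it. The comparison with and without type shows how far the estimate moves, and the E-value then applies to the confounding that remains.

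### Under a two-sided 5% test, 4330 patients give about 86% power rather than 90% (about 4,920 are needed), and the protocol disagrees with itself on whether there is one primary outcome or two

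*Protocol*

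**What the plan says.** All of this is in Protocol section 5, WP4, under Primary care.

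- **Outcomes.** "Our primary outcomes will be patients revisiting the general practice within 7 days or 15 days". This is plural, with two windows.
- **Outcome powered.** "Our power calculation is based on the primary outcome, revisiting general practice within 7 days". This is singular, with one window.
- **Inputs.** "10% of patients consulting a permanent GP return within that time period"; "an increase in the outcome to 15% for locum consultations (OR=1.59"); "Assuming 9 consultations with a permanent GP for 1 consultation with a locum"; "an alpha level of 5" per cent. Neither the sidedness nor the test or formula is given.
- **Result.** "we would need a total of 4330 patients to have 90% power to detect the association".
- **Caveat.** The text concedes that "this approach ignores between-practice variability in both the intercept and the association". It uses the figure only to argue that the available data exceed the need many hundreds of times over. The data source is described as about 1,100 practices, a median of 10 years and millions of patients.

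**The concern.** This is the only sample size in the protocol, and every input needed to check it is printed beside it. A reader who puts those inputs into the standard two-sided comparison of two proportions gets a larger number, and nothing in the text explains the difference. The figure is optimistic even before the clustering that the text openly sets aside.

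The second matter concerns interpretation. If revisits within 7 days and within 15 days point in different directions, or only one shows a difference, the protocol gives two incompatible descriptions of what the primary result is. A later analysis plan would inherit both. No return rate or power is given for 15 days.

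**Working it through.** **Inputs (WP4, Primary care).** Permanent-GP rate p0 = 0.10; locum rate p1 = 0.15; 9 permanent to 1 locum; alpha 5%; power 90%; N = 4330, which is 433 locum and 3,897 permanent patients.

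**Odds ratio.** (0.15/0.85)/(0.10/0.90) = 1.588. The stated 1.59 is correct.

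**Attempt to reproduce 4330, two-sided 5%.** Normal deviates are 1.960 and 1.2816, so (1.960 + 1.2816)² = 10.507.

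1. *Standard pooled formula.* Pooled rate = 0.1 × 0.15 + 0.9 × 0.10 = 0.105.
   - Null term: √(0.105 × 0.895 × (1 + 1/9)) = 0.3231.
   - Alternative term: √(0.15 × 0.85 + 0.10 × 0.90/9) = 0.3708.
   - n(locum) = (1.960 × 0.3231 + 1.2816 × 0.3708)² / 0.05² = 491.5. The total is about 4,916, or 4,920 with 492 locum patients.
2. *Wald formula on the log odds ratio.* ln(1.588) = 0.4626. Variance per patient = 1/(0.1 × 0.1275) + 1/(0.9 × 0.09) = 90.78. N = 10.507 × 90.78 / 0.4626² = 4,457 (4,435 if ln 1.59 is used).
3. *Cruder forms with one variance in both terms.*
   - Pooled variance: 10.507 × 0.105 × 0.895 / (0.09 × 0.05²) = 4,389.
   - Permanent-GP variance only: 10.507 × 0.09 / (0.09 × 0.05²) = 4,203.
4. *Larger variants.* Arcsine 5,060; pooled with continuity correction 5,140; unpooled 5,779.

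None gives exactly 4330. The log-odds formula comes within 3% and the pooled-variance shortcut within 1.4%.

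**Power actually delivered.** A formula's answer is an approximation, so the test itself was checked.

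| Total N | Test at 5% | Power |
|---|---|---|
| 4330 | two-sided, pooled formula: Φ[(0.05 × √433 − 1.960 × 0.3231)/0.3708] = Φ(1.098) | 86.4% |
| 4330 | two-sided Pearson, exact binomial enumeration | 86.4% |
| 4330 | two-sided score and Wald tests, 400,000 simulations | 86.4% each |
| 4,460 | two-sided Pearson, exact (the log-odds formula's own answer, rounded up) | 87.4% |
| 4,900 | two-sided Pearson, exact | 90.1% |
| 4,920 | two-sided Pearson, exact | 90.2% |
| 4330 | one-sided, pooled formula | 91.5% |
| 4330 | one-sided, exact | 91.7% |

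**Effect on the feasibility claim.** The protocol says millions without a figure, so two illustrative totals are assumed.
- 3 million: 3,000,000/4330 = 693 and 3,000,000/4,920 = 610.
- 5 million: 5,000,000/4330 = 1,155 and 5,000,000/4,920 = 1,016.

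Many hundreds remains true either way.

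**Primary outcome.** Side by side, the outcome paragraph has two primary windows and the power paragraph has one. The WP4 primary care text contains no rule that ranks the two windows or says how they combine.

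**The case against.** The strongest defence is that the protocol states neither sidedness nor formula, so a two-sided test is the reviewer's assumption. At one-sided 5% the figure is adequate. Among two-sided approximations, results run from about 4,200 to 5,800, and 4330 lies inside that range. The log-odds form, which suits the quoted odds ratio and the planned logistic model, comes close. This stands in part. A reader might infer that 4330 is a flat arithmetic error that no method could produce, and the document does not support that.

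Closeness to an approximate formula does not deliver the power, however. The log-odds formula's own answer has only 87.4% exact power, and the simulated two-sided Wald test at 4330 has 86.4%. An unqualified 5% is normally read as two-sided, and RQ3 asks how locum and permanent doctors compare and what differences exist, without a direction.

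It is also fair to say that no decision depends on the number and that clustering is already disclosed. Both stand. A reader might infer that the study is underpowered or that the claim of ample data falls. Neither follows, because the database is fixed and very large.

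On the two windows, co-primary outcomes are legitimate and multiplicity rules are often left to the analysis plan. A reader might infer a false-positive rate near 9.8% from two tests at 5% (1 − 0.95² = 0.0975). That figure assumes independent tests. Every revisit within 7 days is also a revisit within 15, so it does not apply here. What remains is the disagreement between two current statements in the protocol.

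**Conclusion.** The point holds in a limited form and is minor. With the protocol's own inputs and a two-sided 5% test, 4330 patients give about 86% power, and 90% needs about 4,900 to 4,920, some 13 to 14% more (4,900/4330 = 1.13; 4,920/4330 = 1.14), ignoring clustering. This rests on the two-sided reading, which is usual and fits RQ3 but is not written down; under a one-sided 5% the stated figure would be sufficient. Feasibility and the closing claim about the size of the data are unaffected.

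The mismatch between two primary outcomes and one is certain on the text and does not depend on any convention. It matters more than the arithmetic, because it decides which result is reported as primary.

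**What to change.** 1. Restate the power sentence along these lines: about 4,920 patients give 90% power for 10% against 15% at 9:1 with a two-sided 5% test (4330 gives about 86%), ignoring clustering. If a one-sided test was intended, say so and justify it against RQ3. In either case name the test or formula.
2. Reconcile the outcome and power paragraphs. One option is to name the powered 7-day revisit as the single primary outcome and list 15 days as secondary. Another is to keep both as primary and state how they are read together.

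Both changes are wording only. No extra patients or data are needed, and the analysis models do not change. The stated sample size becomes slightly less favourable.

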### WP4: Collection and analysis of existing/routine quantitative data sets to compare locum and permanent doctor practice/performance in primary and secondary care (RQ3)

Most routine/existing NHS datasets do not contain sufficient information to distinguish reliably between care provided by locum and non-locum doctors, and so our approach to quantitative analysis makes careful and informed use of selected datasets in which our pilot work has established this analysis is feasible, in order to address RQ3. Locum doctors can be identified either where the staff role is explicitly coded in the data set as a locum, or where records contain medical staff identifiers which can be linked to staffing/HR databases. However, especially in team settings where care may be provided by a number of medical staff including both locums and permanent doctors, it is difficult both to identify and to distinguish the distinctive contribution of locum doctors. For example, an activity (such as admission, discharge, test ordering, prescribing, operative procedure, etc) may be recorded by one member of a team (whether a locum or permanent doctor) but may have been initiated by another.

For this reason, out our quantitative analyses will focus primarily on primary care, where the quality of data is high, locum information is known to be reliably collected and available in CPRD, and the attribution of activities to individual doctors (whether permanent or locum) is less problematic. However, we also set out plans for a more limited feasibility study in

secondary care, using Electronic Patient Record (EPR) data from one NHS trust with the capacity to extend the analysis to others.

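### Antibiotic prescribing is compared over all sampled consultations with no allowance for why the patient came, so acute case-mix alone can produce a locum difference; the safety indicators share the risk in smaller form

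*Protocol*

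**What the plan says.** All of this is in Protocol section 5, WP4, Primary care, unless noted.

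- **Outcomes.** The secondary outcomes include "antibiotic prescriptions, and validated prescribing safety indicators (as established measures of clinical performance and quality of care". The remark about clinical performance and quality belongs to the indicators, not to antibiotics.
- **Population.** Within each financial year "our population will comprise of patients registered with a CPRD general practice for whole of the year".
- **Unit.** The annual sampling rule reads: "we will randomly select one consultation for each patient, and then align all the outcomes and covariates to that specific event date for the patient".
- **Analysis set.** The first design, declared primary, "will involve a multi-level regression on all randomly selected consultation events, which will be used to obtain adjusted estimates". The second design adds propensity score matching on the available covariates.
- **Count outcomes.** "if we identify that numerous indicators tend to apply to visits, we will use multi-level mixed effects Poisson or negative binomial regression models instead".
- **Adjustment.** Patient covariates are age, sex, deprivation, years registered, earlier visits and 18 conditions, described as "numerous chronic conditions which are well recorded in these databases since they are part of the Quality and Outcomes Framework". Infection, reason for consultation and current medication are not listed. Consultation type, length and weekday are to be described but not modelled.
- **Acknowledged confounding.** The protocol thinks locums may handle more urgent requests. It says its covariates control this only in part, and it plans cautious interpretation and an E-value.

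**The concern.** An antibiotic is mostly a response to an infection. Measured over all consultations, the prescribing rate is the share of consultations that are for infection multiplied by the share of infections treated. Only the second factor is a decision of the doctor. If urgent work goes to locums and contains more infections, the first factor differs by GP type, and nothing in the model represents it. Consultation type, the nearest proxy the protocol names, is left out. A case-mix difference could then be published as a difference in locum prescribing.

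A safety indicator has a similar structure: it can be triggered only by a patient whose diagnosis or other medication makes the drug hazardous. If indicators were modelled over every sampled consultation, or summed without regard to how many could apply, opportunity and error would be mixed. Diagnoses are partly in the covariate list; medication is not.

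**Working it through.** **The plan's own figures.** The protocol powers the 7-day revisit outcome for 10% against 15%. The odds ratio is (0.15/0.85)/(0.10/0.90) = 1.588, which agrees with the stated 1.59. The stated total of 4,330 is approximated within 3% by a two-sided Wald formula on the log odds ratio (4,457). The usual pooled two-sided formula gives 4,920. Nothing below depends on that total; it serves only as a yardstick of size.

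**Assumed inputs.** The protocol gives no infection or eligibility shares, so these are assumptions. Let e be the share of sampled consultations for infection (or the share of eligible patients) and q the prescribing probability within that set, equal in both GP groups. Everyone else has no event. Then:

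- rate over all consultations = e × q
- OR = [e_L q/(1 − e_L q)] / [e_P q/(1 − e_P q)], with L for locum and P for permanent
- OR within the infection or eligible set = 1.00 by construction

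**Antibiotics, q = 50%.**

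| Infection share, permanent v locum | Rate, permanent v locum | Unadjusted OR |
|---|---|---|
| 15% v 18% | 7.5% v 9.0% | (0.09/0.91)/(0.075/0.925) = 1.22 |
| 15% v 25% | 7.5% v 12.5% | (0.125/0.875)/(0.075/0.925) = 1.76 |
| 20% v 30% | 10% v 15% | 1.59 |
| 20% v 15% | 10% v 7.5% | 0.73 |

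The third row gives the same odds ratio that the protocol calls meaningful for its primary outcome. The fourth shows that the sign reverses if locums see fewer infections.

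**Safety indicators, q = 5%, if patients who are not eligible were included.**

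| Eligible share, permanent v locum | Rate, permanent v locum | Unadjusted OR |
|---|---|---|
| 30% v 25% | 1.5% v 1.25% | 0.83 |
| 30% v 20% | 1.5% v 1.0% | 0.66 |

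Age, sex and the 18 conditions would move these towards 1. What remains is the part of eligibility that depends on medication.

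**Does the E-value deal with it?** For a risk ratio of 1.5 the E-value is 1.5 + √(1.5 × 0.5) = 2.37. It is calculated as if the confounder were equally strongly related to exposure and outcome. Where the outcome hardly occurs without the condition, as assumed here, the link with outcome is close to unlimited. A prevalence ratio of 1.5 between GP groups is then enough to explain a risk ratio of 1.5. An E-value of 2.37 would look more reassuring than it should.

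**Size after restriction.** With a 9:1 mix and shares of 15% and 25%, infection consultations are 0.9 × 15% + 0.1 × 25% = 16% of the sample. For indicators, 4,330 eligible patients would need 4,330/0.10 = 43,300 sampled consultations at a 10% eligible share, or 4,330/0.01 = 433,000 at 1%. The protocol expects millions of patients.

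**The case against.** The strongest reply concerns the safety indicators. A reader might infer that the plan scores ineligible patients as safe. No sentence says so. The indicators are called validated, and validated indicators normally carry their own denominators, which a statistical analysis plan may spell out. The phrase about all selected consultations can be read as a contrast with the matched design. The count-model sentence only chooses a model family; it neither includes nor excludes an offset. The reference attached to the indicators concerns hospital prescribing by its listed title and cannot be consulted here, so it settles nothing. This objection stands: for indicators the fault is conditional.

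A reader might also infer that repeats begun by another GP invalidate attribution. The protocol's statement that an activity "may be recorded by one member of a team (whether a locum or permanent doctor) but may have been initiated by another" is about team settings. Attribution in primary care is described there as less of a problem, and CPRD has consultation and staff identifiers. Re-issuing a hazardous item is also a prescribing decision. That supports a sensitivity analysis, not a change of main outcome.

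Further, the odds ratios above are unadjusted and rest on invented shares, and the protocol already admits confounding by urgency. Both points are fair. They do not remove the antibiotic problem: the covariates describe chronic disease and background, not why the patient came that day, and matching uses the same available covariates.

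Finally, restricting to infection codes has its own weakness. The index GP enters the code, possibly in order to justify the prescription, so coding may differ by GP type. This stands, and it is why the restricted analysis should not be the sole main analysis.

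**Conclusion.** The point holds for antibiotics. As written, that comparison mixes acute case-mix with prescribing, and neither the covariates nor the E-value separates them. Under equal prescribing, unadjusted odds ratios of 1.22 to 1.76 arise from assumed infection shares of 15% against 18% to 25% with half treated. These figures illustrate the mechanism; they do not estimate the bias in the adjusted analysis. The direction rests on two assumptions: that locums do take more urgent work, which the protocol offers only as a possibility, and that urgent work contains more infections.

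For the safety indicators the conclusion is weaker. The same risk exists, in smaller and partly adjusted form, if they are modelled over all sampled consultations or as a raw count. It would be wrong to say that the plan certainly does this, or that its indicator results would merely reflect the patients seen. These are secondary outcomes and the primary revisit outcome is not touched, so the change is advisable rather than critical.

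**What to change.** Amend the model and design paragraphs of WP4, Primary care:

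1. **Antibiotics.** Also analyse prescribing among consultations with a recorded infection diagnosis or symptom code, and report it beside the all-consultation rate. Claim a locum effect on prescribing only if the two agree. Compare infection-coding rates between locum and permanent GPs, because coding may itself differ.
2. **Safety indicators.** Model each indicator only in patients who meet its risk condition at the index date. In any count model, include log(number of indicators for which the patient is eligible) as an offset.
3. **Attribution.** As a sensitivity analysis, limit indicator events to items issued under the index consultation and staff identifier, with new starts and repeats shown separately.

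The protocol says that CPRD holds the diagnoses, prescriptions and identifiers needed, so the work is mainly code lists and programming. The price is fewer consultations in these analyses and dependence on diagnostic coding.
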